### 9.5.1 Immunogenicity and Safety Measurements Assessed and Flow Chart

**Table 2: Schedule of Study Procedures – Oral & Sublingual Cohorts**

Oral and Sublingual cohorts												Unscheduled visit, upon investigator judgement	Early Termination 
Study Visit (V)	screen	1	2	3	4	5	6	7	8	9			
Study Day	-7 to -4	1	8	15	22	29	36	57	114	209			
Window			±1d	±2d	±1d	±2d	±1d	±3d	±1w	±2w			
Study Week		0	1	2	3	4	5	8	16	30			
Informed Consent	X												
Confirm Ongoing Consent		X	X	X	X	X	X	X	X	X			
Eligibility Review	X	X	X	X	X	X	X	X	X				
Collection of demographics	X												
Medical History	X	X	X	X	X	X	X	X	X	X		[X]	
Concomitant Medications	X	X	X	X	X	X	X	X	X	X		[X]	
Physical Exam	X	X 			[X]								
Vitals Signs	X 		[X]										
Urine pregnancy test 	X	X		X		X							
VACCINATION		#1		#2		#3							
Pre-vaccination & Post-vaccination assessment		X 		X 		X 							
Memory Aid and thermometer (d)istribute, (c)ollect Memory Aid		d	C	d	C	D	c					[c] 	
Confirm date & time of next Visit		X	X	X	X	X	X	X	X				
Adverse Event (AE)/Serious AE review		X	X 	X	X 	X	X 	X 	X 	X 	X 	X	
Screening stool	X												
Saliva/Oral Fluid for Ab		X	X	X	X	X	X	X					
Stool for ELISA Ab		X	X	X	X	X	X	X					
Stool for future use (Microbiome studies)	X	X	X	X	X	X	X	X					
Clinical labs/chemistry	2 mL							2 mL	2 mL				
Blood-Serum for ELISA Ab & Neut.		3 mL	2 mL	3 mL	2 mL								

*Also may occur:  
Stool culture when indicated;  
Exam and Photo of local reactogenicity when indicated*

Oral and Sublingual cohorts											
Blood-PBMC for ASC		2 mL	2 mL	2 mL	2 mL	2 mL	2 mL				
Blood-PBMC for ASC w/ homing			2 mL		2 mL		2 mL				
Blood-PBMC for ALS		2 mL	2 mL	2 mL	2 mL	2 mL	2 mL				
Blood-PBMC for Memory B assays		8mL			5 mL		5 mL	5 mL	5 mL		
Blood-PBMC for effector T cell assays	13 mL				8mL		7 mL	7 mL	8 mL	10 mL	
Store plasma from PBMC		X	X		X		X	X	X	X	
Total Blood Volume up to ~140 mL/participant	15 mL	15 mL	8 mL	6 mL	21 mL	6 mL	22 mL	17 mL	15 mL	15 mL	10 mL

[ ] Make every effort to collect at Early Termination visit. If not collected, this will not result in a protocol deviation.

review for Serious Adverse Events only

Targeted physical examination, if indicated based on review of medical history

Vital signs: collect oral temperature, pulse, and blood pressure

Urine pregnancy test required for all women

Exam at end of 30 min observation period post-vaccination for SL and ID, at end of a 90 min observation period for Oral

Review to include assessments of: 1) injection site necrosis within 7 days of vaccination, 2) urticaria, laryngospasm, bronchospasm, or anaphylaxis determined to be related to vaccine and within 7 days of vaccination, 3) facial nerve neuropathy, confirmed by an investigator and determined to be related to vaccine.

Assess reactogenicity and review memory aid if early termination occurs within 7 days of any vaccination

AE assessment to include (as applicable): 1) Assess reactogenicity (if within 7 days of last vaccination), unsolicited non-serious AE information (if within 28 days of last vaccination), or any SAE information (anytime within study) 2) Upon judgement of the clinical investigator, clinical laboratory assessments may be performed to evaluate an AE and medications (e.g. analgesics) may be recommended to treat an AE.

Visits 1-7: Provide instructions to women participants to avoid pregnancy through the 28 days from receipt of the last dose of vaccine.

Early Termination Visit is to include: assess reactogenicity and review memory aid if early termination occurs within 7 days of any vaccination; assess for SAE during all early termination visits; obtain serum samples for laboratory safety assays if visit occurs <28 days after third vaccination.

**Table 3: Schedule of Study Procedures – Intradermal Cohort**

Intradermal Cohort											Unscheduled visit, upon investigator judgement	Early Termination 
Study Visit (V)	screen	1	2	3	4	5	6	7	8	9		
Study Day	-7 to -4	1	8	22	29	43	50	71	128	223		
Window			±1d	±2d	±1d	±2d	±1d	±3d	±1w	±2w		
Study Week		0	1	3	4	6	7	10	18	32		
Informed Consent	X											
Confirm Ongoing Consent		X	X	X	X	X	X	X	X	X		
Eligibility Review	X	X	X	X	X	X	X	X	X			
Collection of demographics	X											
Medical History	X	X	X	X	X	X	X	X	X	X		[X]
Concomitant Medications	X	X	X	X	X	X	X	X	X	X		[X]
Physical Exam	X	X 	X 	X 	X 	X 	X 	X 	X 			[X]
Vitals Signs	X 	X 	X 	X 	X 	X 	X 	X 	X 	X		[X]
Urine pregnancy test 	X	X		X		X						
VACCINATION		#1		#2		#3						
Pre-vaccination & Post-vaccination assessment		X 		X 		X 						
Memory Aid and thermometer (d)distribute, (c) collect Memory Aid		d	c	d	c	d	c					[c] 
Confirm date & time of next Visit		X	X	X	X	X	X	X	X			
Adverse Event (AE) / Serious AE review		X	X 	X	X 	X	X 	X 	X 	X 	X 	X
Screening stool	X											
Saliva/Oral Fluid for Ab		X	X	X	X	X	X	X			Also may occur: Stool culture when indicated; Exam and Photo of local reactogenicity when indicated	
Stool for ELISA Ab		X	X	X	X	X	X	X				
Stool for future use (Microbiome studies)	X	X	X	X	X	X	X	X				
Clinical labs/chemistry	2 mL						2 mL	2 mL				
Blood-Serum for ELISA Ab & Neut.		3 mL	2 mL	2 mL	2 mL	2 mL	2 mL	3 mL	2 mL			

Intradermal Cohort										
Blood-PBMC for ASC		2 mL	2 mL	2 mL	2 mL	2 mL	2 mL			
Blood-PBMC for ASC w/ homing			2 mL		2 mL		2 mL			
Blood-PBMC for ALS		2 mL	2 mL	2 mL	2 mL	2 mL	2 mL			
Blood-PBMC for Memory B assays		8mL			5 mL		5 mL	5 mL	5 mL	
Blood-PBMC for effector T cell assays	13 mL				8 mL		7 mL	7 mL	8 mL	10 mL
Store plasma from PBMC		X	X		X		X	X	X	
Total Blood Volume up to ~140 mL/participant	15 mL	15 mL	8 mL	6 mL	21 mL	6 mL	22 mL	17 mL	15 mL	15 mL
										10 mL

[ ] Make every effort to collect at Early Termination visit. If not collected, this will not result in a protocol deviation.

review for Serious Adverse Events only

Targeted physical examination, if indicated based on review of medical history

Vital signs: collect oral temperature, pulse, and blood pressure

Urine pregnancy test required for all women

For grade 3 local site reactions, a photo should be taken on a daily basis until the injection site reaction is deemed stable or returns back to a grade 2 or lower severity, if the event occurs within 7 days of an intradermal dose administration

Exam at end of 30 min observation period post-vaccination

Review to include assessments of: 1) injection site necrosis within 7 days of vaccination, 2) urticaria, laryngospasm, bronchospasm, or anaphylaxis determined to be related to vaccine and within 7 days of vaccination, 3) facial nerve neuropathy, confirmed by an investigator and determined to be related to vaccine.

Assess reactogenicity and review memory aid if early termination occurs within 7 days of any vaccination

AE assessment to include (as applicable): 1) Assess reactogenicity (if within 7 days of last vaccination), unsolicited non-serious AE information (if within 28 days of last vaccination), or any SAE information (anytime within study) 2) Upon judgement of the clinical investigator, clinical laboratory assessments may be performed to evaluate an AE and medications (e.g. analgesics) may be recommended to treat an AE.

Visits 1-7: Provide instructions to women participants to avoid pregnancy through the 28 days from receipt of the last dose of vaccine.

Early Termination Visit is to include: assess reactogenicity and review memory aid if early termination occurs within 7 days of any vaccination; assess for SAE during all early termination visits; obtain serum samples for laboratory safety assays if visit occurs <28 days after third vaccination.

### 9.7.1 Sample Size

**Table 4: Sample Size/Probability Estimates**

	Evaluable Vaccinees (N)	Upper 95% Confidence Bound in the Absence of Observed Dose-Limiting AE
Per Cohort	10	30.8%
Per Route a	20	16.8%
Cohorts A-D b	40	8.8%
Cohorts A-F c	60	6.0%

aOral, sublingual or intradermalbReceived all three dosescPlanned prior to safety data review

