The evaluation of immunogenicity will include dmLT-specific antibody responses in serum, fecal, salivary and ALS samples, in addition levels of ASC in circulation will be determined. Memory B cells specific for dmLT will also be evaluated. An in-depth evaluation of effector and memory T cells response, including homing potential, cytokine/chemokine production profile, degranulation capacity, and activation potential, will also be performed. In order to maximize our ability to compare immune responses between US and Bangladesh studies, the timing of the sample collections for the immunological assays needs to be comparable. The timing of the specimen collection for the immunological assays were selected based on previous

DMID-funded dmLT studies conducted in the U.S. (i.e., DMID protocols 09-0066 and 12-0023) and the ongoing study 13-0013.

Additional participants may be enrolled to ensure there are at least 11 evaluable participants (10 vaccinees and 1 placebo) in each of the cohorts (cohorts A through I). Evaluable participants are defined as completing all 3 doses of vaccine and providing both safety and protocol-required specimens through at least 7 days after the third dose of vaccine. If additional participants are required, to maintain blinding, treatment assignments of additional participants are to be determined by Emmes.

The duration of the study for each participant will be up to 9 months (inclusive of the screening period through 6 months after the third dose of vaccine, plus a 2-week window on the last visit), depending on the route of dmLT administered. Details on the study procedures, evaluations, and study schedule are in [Sections 7, 8](#) and [Appendix A](#), respectively.

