## 4. INVESTIGATIONAL PLAN

### 4.1. Overall Study Design and Plan

This is a phase 1, single center, randomized, double-blinded, placebo controlled, dose escalation clinical trial in which 135 healthy males and non-pregnant females ages 18-45 who met all eligibility criteria were to receive 3 doses of either dmLT vaccine or placebo, randomized in a 4:1 ratio. Cohort A and Cohort B participants received study product via oral administration. Cohort C and Cohort D participants received study product via sublingual administration. Cohort E participants received two of three planned doses of study product via intradermal administration prior to the study being terminated due to the COVID-19 pandemic. No participants were enrolled in planned Cohorts F, G, H, or I. Participants were screened by history, physical exam, and clinical laboratory tests, including a urine or serum pregnancy test for women of childbearing potential. A schematic of the planned study design is presented in [Table 1](#).

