#### **4.4.3. Method of Assigning Subjects to Treatment Groups (Randomization)**

The randomization code was prepared by the Statistical and Data Coordinating Center (SDCC), Emmes. Enrollment/randomization were performed through the enrollment module in the electronic data capture system, maintained by the SDCC.

For each cohort, eligible participants were randomized and assigned in a 4:1 ratio to dmLT (n = 12) or placebo (n = 3) groups. The randomization was based on a variable blocked scheme to provide an approximately balanced allocation to the treatment groups during the study.

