## 5. SAMPLE SIZE CONSIDERATIONS

The sample size for each cohort was chosen based on the number of participants deemed appropriate for a Phase 1 study in which the vaccine has had limited experience by the different routes of administration in humans. Sample size was limited to at least 11 evaluable participants and up to 15 participants for each cohort (each of the nine planned cohorts A through I).

The DMID Data and Safety Monitoring Board (DSMB) was scheduled to review cumulative data after Cohorts A through F had completed safety data through 7 days post-third dose of vaccine. At which time each cohort had been expected to have at least 10 evaluable vaccinees (10 per cohort). Among the 10 vaccinees per dose, the absence of a dose-limiting AE provides for an upper 95% exact (Clopper-Pearson) confidence bound of 30.8%. The absence of a dose-limiting AE among 20 vaccinees per route (e.g., combining safety data from Cohort A and B) provides for an upper 95% confidence bound of 16.8%. If at the time of data review, there had been no dose-limiting AEs among 60 vaccinees (e.g., combining safety data from Cohorts A through F), this would have provided an upper 95% confidence bound of 6.0% (Table 4). There were no dose-limiting AEs among the 40 vaccinees (Cohort A through D) who received all three planned doses which provides an upper 95% confidence bound of 8.8%.

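### SAP Table 4 applies the 20-vaccinee per-route bound of 16.8% to the intradermal route, not marked as planned, although that route has no three-dose evaluable vaccinees

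*SAP*

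**What the plan says.** SAP Section 5 and Table 4 give upper bounds on the dose-limiting AE rate for several group sizes. The column is headed "Upper 95% Confidence Bound in the Absence of Observed Dose-Limiting AE".

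- Per cohort, N = 10: 30.8%.
- Per route, N = 20: 16.8%. Footnote a defines the routes as "Oral, sublingual or intradermal".
- Cohorts A-D, N = 40: 8.8%. Footnote b says these vaccinees had all three doses.
- Cohorts A-F, N = 60: 6.0%. Footnote c marks this row as planned.

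Section 5 has the matching sentence, "The absence of a dose-limiting AE among 20 vaccinees per route (e.g., combining safety data from Cohort A and B"), written in the present tense.

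The same SAP describes what happened on the intradermal route. Section 4.1 states: "No participants were enrolled in planned Cohorts F, G, H, or I". Sections 4.1, 4.4.1, 4.4.5 and 15 say that Cohort E had two of its three planned doses. Section 15 adds that its Visits 6 through 9 were not held. By design each cohort was "assigned in a 4:1 ratio to dmLT (n = 12) or placebo (n = 3) groups" (Section 4.4.3).

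Protocol Section 4 sets the condition for the N column: "Evaluable participants are defined as completing all 3 doses of vaccine", with safety data and specimens through at least 7 days after the third dose.

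**The concern.** The SAP was written after the trial stopped, and Table 4 was revised to reflect that: the A-D row reports an achieved group and the A-F row is labelled as planned. The per-route row has neither label. A reader of the table alone has nothing to show that one of the three named routes never reached the stated N.

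Safety by route is the primary objective. Table 4 carries a study-report section number (9.7.1), so it is meant to go into the clinical study report. There, the row could be read as saying that an absence of dose-limiting AEs by the intradermal route excludes rates above 16.8%. The intradermal data cover one cohort, two doses and 0.3 µg only, and contain no three-dose exposure at all.

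**Working it through.** **Inputs**

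- Method: Section 5 refers to an "upper 95% exact (Clopper-Pearson) confidence bound of 30.8" percent for 10 vaccinees. It does not say whether the limit is one-sided or two-sided.
- Events: zero, from the Table 4 column heading.
- N per route: 20, which is two cohorts of 10.
- Intradermal cohorts enrolled: one (E). Doses given: two of three.
- Cohort E dmLT recipients: 12 by allocation. No dosed count is reported.

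**Step 1. Reproduce the printed figures.** With zero events the two-sided exact 95% upper limit is 1 − 0.025^(1/n).

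| n | 1 − 0.025^(1/n) | Printed |
|---|---|---|
| 10 | 30.85% | 30.8% |
| 20 | 16.84% | 16.8% |
| 40 | 8.81% | 8.8% |
| 60 | 5.96% | 6.0% |

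All four agree within rounding. The one-sided form, 1 − 0.05^(1/n), gives 25.9% at n = 10 and 13.9% at n = 20 and does not match. The table therefore uses two-sided limits.

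**Step 2. Count the evaluable intradermal vaccinees.** Evaluable requires three doses. No Cohort E participant had a third dose and Cohorts F and I were never enrolled, so the number is 0. Neither the 20 per route nor the 10 per cohort is met, and no informative three-dose bound exists.

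**Step 3. What a two-dose bound would be if no event occurred.**

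- n = 12 (full allocation dosed): 1 − 0.025^(1/12) = 26.46%
- n = 11: 28.49%
- n = 10 (the per-cohort number Table 4 uses): 30.85%

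Against the printed figure, 26.46 − 16.84 = 9.6 points and 30.85 − 16.84 = 14.0 points. Even a one-sided limit at n = 12, which is not the table's convention, is 22.1%.

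**The case against.** The strongest reply is that this is a planning row, correctly calculated. It comes from Protocol Section 11.2, and Section 5 illustrates it with Cohorts A and B only. The table is conditional on no event being seen. The shortened intradermal arm is disclosed repeatedly, including in the footnotes to SAP Table 1. Intradermal solicited-event rates will be reported with exact intervals for Cohort E in SAP Tables 103 and 104, so safety by route will not be read from Table 4 alone. No hypothesis test is planned, the study has ended, and no decision depends on this row.

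Much of that stands. There is no calculation error, and the consequence is limited to how precision is described. It does not clear the row. The explicit mention of the intradermal route is the SAP's own, in a table that otherwise separates planned from achieved. Disclosure elsewhere does not correct a table that may be read by itself.

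Three stronger readings are tempting, and the documents do not support them.

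- A reader might infer that the true intradermal bound is 26.5%. That needs 12 recipients dosed and no events. The 12 is an allocation, and the SAP's statement of no dose-limiting AEs covers only the 40 vaccinees of Cohorts A-D.
- A reader might enter Cohort E as N = 12 in the existing column. That column counts evaluable vaccinees, and Cohort E has none.
- A reader might infer that the intradermal route is expected to produce the most local reactions. Protocol Section 2.2.1 lists possible injection-site reactions but does not rank the routes. The comparison in Section 2.1 is with transcutaneous delivery of a different product.

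**Conclusion.** The point holds as a missing qualifier and a wrong scope, not as an arithmetic error. For the intradermal route, N = 20 and 16.8% describe a group that does not exist, and the per-cohort row does not describe Cohort E either. That conclusion rests only on the SAP's account of enrolment and dosing and on the protocol's definition of evaluable.

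The size is conditional. With zero events, a two-dose bound at 0.3 µg would lie between 26.5% (12 dosed) and 30.8% (10 dosed). These are illustrations under stated assumptions, because neither the dosed count nor the event count for Cohort E is reported. The per-route figure is not disputed here for the oral and sublingual routes.

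**What to change.** Limit the per-route row, footnote a and the Section 5 sentence ("The absence of a dose-limiting AE among 20 vaccinees per route") to oral and sublingual. Alternatively, keep the intradermal route and mark its figure as planned and not achieved. Add a footnote that no intradermal participant met the three-dose evaluable definition, so neither the per-cohort 10 nor the per-route 20 applies to that route.

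An intradermal precision row is optional. If one is added, label it as two doses, 0.3 µg, dosed (not evaluable). Use the actual number of dmLT recipients dosed and the observed event count. Until those are confirmed, present the bound only as conditional on zero events: 26.5% if 12 were dosed, 30.8% if 10.

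The cost is a row label, a footnote and a sentence, plus the optional row. The only downside is a less favourable stated bound for the intradermal route.

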## 10.2 Protocol Deviations

**Table 5: Distribution of Protocol Deviations by Category, Type, and Treatment Group – Oral & Sublingual Cohorts**

Category	Deviation Type	Cohort A: Oral 5 µg dmLT (N=X)		Cohort B: Oral 25 µg dmLT (N=X)		All Oral Cohorts: Placebo (N=X)		All Oral Route Subjects (N=X)		Cohort C: Sublingual 5 µg dmLT (N=X)		Cohort D: Sublingual 25 µg dmLT (N=X)		All Sublingual Cohorts: Placebo (N=X)		All Sublingual Route Subjects (N=X)	
		No. of Subj.	No. of Dev.	No. of Subj.	No. of Dev.	No. of Subj.	No. of Subj.	No. of Dev.	No. of Subj.	No. of Dev.	No. of Subj.	No. of Dev.	No. of Subj.	No. of Dev.	No. of Subj.	No. of Dev.	
Eligibility/ enrollment	Any type																
	Did not meet inclusion criterion	x	x	x	x	x	x	x	x	x	x	x	x	x	x	x	x
	Met exclusion criterion																
	ICF not signed prior to study procedures																
	Other																
Treatment administration schedule	Any type																
	Out of window visit																
	Missed visit/visit not conducted																
	Missed treatment administration																
	Delayed treatment administration																
	Other																
Follow-up visit schedule	Any type																
	Out of window visit																
	Missed visit/visit not conducted																
	Other																

**Table 5: Distribution of Protocol Deviations by Category, Type, and Treatment Group (continued)**

Category	Deviation Type	Cohort A: Oral 5 µg dmLT (N=X)		Cohort B: Oral 25 µg dmLT (N=X)		All Oral Cohorts: Placebo (N=X)		All Oral Route Subjects (N=X)		Cohort C: Sublingual 5 µg dmLT (N=X)		Cohort D: Sublingual 25 µg dmLT (N=X)		All Sublingual Cohorts: Placebo (N=X)		All Sublingual Route Subjects (N=X)	
		No. of Subj.	No. of Dev.	No. of Subj.	No. of Dev.	No. of Subj.	No. of Subj.	No. of Dev.	No. of Subj.	No. of Dev.	No. of Subj.	No. of Dev.	No. of Subj.	No. of Dev.	No. of Subj.	No. of Dev.	
Protocol procedure/ assessment	Any type																
	Incorrect version of ICF signed																
	Blood not collected																
	Urine not collected																
	Stool not collected																
	Other specimen not collected																
	Too few aliquots obtained																
	Specimen result not obtained																
	Required procedure not conducted																
	Required procedure done incorrectly																
	Study product temperature excursion																
	Specimen temperature excursion																
	Other																
Treatment administration	Any type																
	Required procedure done incorrectly																

**Table 5: Distribution of Protocol Deviations by Category, Type, and Treatment Group (continued)**

Category	Deviation Type	Cohort A: Oral 5 µg dmLT (N=X)		Cohort B: Oral 25 µg dmLT (N=X)		All Oral Cohorts: Placebo (N=X)		All Oral Route Subjects (N=X)		Cohort C: Sublingual 5 µg dmLT (N=X)		Cohort D: Sublingual 25 µg dmLT (N=X)		All Sublingual Cohorts: Placebo (N=X)		All Sublingual Route Subjects (N=X)	
		No. of Subj.	No. of Dev.	No. of Subj.	No. of Dev.	No. of Subj.	No. of Dev.	No. of Subj.	No. of Dev.	No. of Subj.	No. of Dev.	No. of Subj.	No. of Dev.	No. of Subj.	No. of Dev.	No. of Subj.	No. of Dev.
	Study product temperature excursion																
	Other																
Blinding policy/ procedure	Any type																
	Treatment unblinded																
	Other																

Note: N= Number of subjects in the Safety Population

Tables with similar format:

**Table 6: Distribution of Protocol Deviations by Category, Type, and Treatment Group – Intradermal & Pooled Cohorts**

*[Implementation note: Treatment groups are Cohort E: Intradermal 0.3 µg dmLT (N=X), Cohort E: Intradermal Placebo (N=X), and All Intradermal Route Subjects (N=X). All Subjects (N=X) will be added at the end.]*

## 12.2.2 Displays of Adverse Events

**Table 7:      Solicited Adverse Event Grading Scale**

Solicited Adverse Event	Normal	Mild (Grade 1)	Moderate (Grade 2)	Severe (Grade 3)
Fever (Oral °C)	35-37.9	38.0 to 38.4	38.5 to 38.9	≥39.0
Feverishness (Chills/Shivering/Sweating)	none	Mild, but no interference with function	Some interference with daily activity	Significant interference, prevents daily activity
Fatigue (Tiredness)	Normal activity reduced slightly	Normal activity decreased 25-50%	Unable to perform daily activity	Urgent care visit or hospitalization
Malaise (General Unwell Feeling)	No interference with daily activity	Some interference with daily activity	Significant interference with daily activity	Urgent care visit or hospitalization
Myalgia (Body/Muscle Aches)	Mild, but no interference with function	Moderate, interferes with function, but not with daily activity	Severe, interferes with daily activity	Severe and disabling, unable to perform daily activity
Headache	Mild and brief or easily tolerated	Moderate with limited effect to daily activity	Severe and prevents daily activity	Urgent care visit or hospitalization
Diarrhea	Normal or 1-2 loose stool per 24 hr	3 loose stools per 24 hr	4-7 loose stools per 24 hr	8 or more loose/watery stools per 24 hr or requires outpatient IV hydration, ED visit or hospitalization for diarrhea
Nausea	none	Mild, but no interference with activity or intake	Moderate, interferes with activity or intake	Severe, unable to perform activity or no intake
Vomiting	none	1-2 episodes per 24 hr.	3-4 episodes per 24 hr.	≥5 episodes per 24 hr.
Abdominal Discomfort	No interference with daily activity	Some interference with daily activity	Significant interference with daily activity	Urgent care visit or hospitalization
Irritation of Oral Cavity (Mouth Pain/Sores)	none	Mild or transient, no limitation of oral intake	Moderate, slight interference with oral intake	Severe, unable to tolerate oral intake
Facial Nerve Disturbance	none	Mild or transient, no limitation	Moderate disturbance but no overt facial nerve palsy	Severe, obvious facial nerve palsy
Injection Site Pain	none	Aware of pain but no interference with activity	Slight interference with activity, may require analgesic	Pain that prevents daily activity
Injection Site Redness	none	Less than 5x5 cm	Greater than 5x5 cm but less than 9x9 cm	Greater than 9x9 cm
Injection Site Swelling	none	Less than 5x5 cm	Greater than 5x5 cm but less than 9x9 cm	Greater than 9x9 cm or ulceration or necrosis
Injection Site Bruising (Ecchymosis)	none	Less than 5x5 cm	Greater than 5x5 cm but less than 9x9 cm	Greater than 9x9 cm
Injection Site Itching	none	Aware of sensation but no interference with activity	Slight interference with activity, may require medication	Itching that prevents daily activity
Injection Site Induration (limited to the dermal layer)	none	Less than 5x5 cm	Greater than 5x5 cm but less than 9x9 cm	Greater than 9x9 cm
Injection Site Hypo/Hyperpigmentation	none	Less than 1x1 cm	Greater than 1x1 cm but less than 5x5 cm	Greater than 5x5 cm
Injection Site Vesicles	none	≤5 vesicles and localized to injection site	>5 vesicles and localized to injection site	Any number of vesicles which are generalized in distribution
Injection Site Hardened Mass (deeper than dermal layer)	none	Less than 1x1 cm	Greater than 1x1 cm but less than 5x5 cm	Greater than 5x5 cm

**12.4.1 Individual Laboratory Measurements and Abnormal Laboratory Values****Table 8: Laboratory Adverse Event Grading Scale**

Solicited Lab AEs	Grade 1 – Mild	Grade 2 – Moderate	Grade 3 - Severe
WBC, Decreased (cells x10  /Liter)	2.0 – 3.9	1.5 – 1.9	≤1.4
WBC, Increased (cells x10  /Liter)	11.1 – 15.0	15.1 – 20.0	≥20.1
ANC, Decreased (cells x10  /Liter)	1.0 – 1.9	0.75 – 0.99	≤0.74
Hemoglobin, female (mg/dL)	9.0- 9.4	8.0 - 8.9	6.5 – 7.9
Hemoglobin, male (mg/dL)	10.0 - 10.9	9.0 – 9.9	7.0 – 8.9
Platelets (cells x 10  /Liter)	100 – 149	50 – 99	≤49
Creatinine (μmol/Liter)	1.1 – 1.3 x ULN*	>1.3 – 1.8 x ULN*	>1.8 – 3.4 x ULN*
ALT (SGPT) (U/L)	1.25 – 2.5 x ULN*	>2.5 – 5.0 x ULN*	>5.0 – 10.0 x ULN*
Albumin (g/dL)	2.8 - 3.1	2.5 - 2.7	< 2.5

\*ULN = upper limit of normal, from the laboratory reference range

